2.3.1 Potential Risks

This study poses minimal risk to participants. Study participation is completely voluntary, and participants may discontinue participation at any time without prejudice. As with any study, there is the potential for loss of confidentiality. Appropriate precautions will be taken to mitigate this risk. These precautions include the use of unique study identifiers for participants when linked with questionnaire data, as well and standard use of password-protected computers and secure networks for data storage. Compliance with all Institutional Review Board (IRB) regulations concerning data collection, data storage, and data destruction will be strictly observed. Data will only be accessible to research personnel and will be stored and coded according to guidelines set forth by the overseeing IRB.

2.3.2 Potential Benefits

Participating dentists have the potential to directly benefit from their reflection on their own knowledge and implementation of substance use screening as they respond to items on the questionnaire. As an indirect benefit to participation, knowledge obtained from the questionnaire has the potential to guide development of future training and implementation tools for use in the dental setting. This questionnaire is intended to provide information regarding existing clinical practices pertinent to addictions screening, brief intervention, and referral to treatment in the dental setting. Dissemination of research results beyond study participants may also benefit the broader dental care community.

3 OBJECTIVES AND OUTCOME MEASURES

3.1 Primary

Objective	Brief Description/Justification of Outcome Measure	Outcome Measured By	Time Frame
The primary objective of this study is to conduct a national survey of dentists to assess knowledge, attitudes, and behaviors related to substance use screening implementation among adolescent, young adult, and adult dental patients.	Although dentists regularly encounter patients with problematic substance use and recognize the importance of screening for substance abuse, they have limited exposure to addictions training and generally lack systems to aid in screening, intervention, and referral to addictions treatment. Self-reported knowledge (prior training experiences), attitudes, and current behaviors regarding screening implementation are critical to understand in guiding development of future training and implementation initiatives.	The primary outcome measures will be assessed by an electronic questionnaire regarding current perspectives and practice behavior related to substance use screening among patients. Specific items (or groups of items) will assess each domain with either dichotomous, Likert scale, frequency, or percentage ratings.	Administration of an electronic questionnaire will be used to measure this outcome.

3.2 Secondary

Objective	Brief Description/Justification of Outcome Measure	Outcome Measured By	Time Frame
The secondary objectives are to identify practitionerand practice-level facilitators and barriers of substance use screening implementation and implementation of early intervention and/or referral strategies (when indicated).	Updated knowledge regarding barriers to screening implementation, particularly implementation among adolescent patient populations, is a critical scientific gap necessary to inform targeted implementation interventions in this arena.	The secondary outcome measures will be assessed by responses provided to an electronic questionnaire regarding practitioners perceived facilitators and barriers to implementing substance use screening, brief intervention, and referral strategies.	Administration of an electronic questionnaire will be used to measure this outcome.

4 STUDY DESIGN

This study is a cross-sectional questionnaire of Network dentists (N=825) practicing across all practice-setting types across the United States. To be eligible for the study, dentists must be enrolled in the Network at Level 2 (limited) or Level 3 (full) participation, currently practicing, and have completed the Enrollment Questionnaire since the start of cycle 3.

The study population will include a stratified random sample of eligible Network dentists. The study sample will be stratified by region. The NCC will be responsible for randomly selecting dentists from within each Network region in proportion to that region's representation in the Network. Network regional quotas will help to ensure that each region has adequate representation within the questionnaire. To provide adequate representation of practitioners working with adolescent patients, pediatric dentists will be oversampled to ensure that a minimum of 50 pediatric dentists participate in the questionnaire.

Eligible Network dentists will be sent an email invitation to participate in the questionnaire study. The questionnaire will take approximately 25-30 minutes to complete and will be administered using the Electronic Data Capture System (EDC) housed at the NCC.

Following the launch of the questionnaire, approximately 50 of the initial questionnaire responders will be selected to complete the electronic questionnaire again (approximately 2 weeks post initial questionnaire completion) to establish test-retest reliability.

Approximately 3 months are estimated to complete recruitment into the study to obtain the desired sample size.

5 STUDY POPULATION

5.1 Participant Inclusion Criteria

A participant must meet all the following criteria:

- Is enrolled in the Network as limited or full network member.
- Has completed or updated an Enrollment Questionnaire within cycle 3.
- Is a dentist licensed in the US to treat patients and treats patients in the US on a recurring basis and is able to receive emails and access online questionnaires.

5.1.1 Participant Exclusion Criteria

Participants are excluded from the study if they:

 Are a graduate student, intern or resident, dental student, dental hygiene student, dental therapy student, dental hygienists, or dental therapist as indicated on the Enrollment Questionnaire.

5.2 Strategies for Recruitment and Retention

Recruitment

As of November 6, 2022, the Network reported 8,077 enrolled dentist (in solo practice) members. Of the dentist members, only 2.7% (221 dentists) endorse a specialty practice in pediatric dentistry. If randomly sampled proportionate to their representation in the Network, fewer than 25 pediatric dentists would likely complete the questionnaire. Given the keen interest in substance use screening implementation among adolescent patients, we will intentionally oversample pediatric dentists for participation in this study (n=50).

The study population will include a stratified (based on regional membership) random sample. Eligible Network dentists will be identified by the network practitioner database managed by the NCC. A random selection of eligible Network dentists will be invited to participate, using a randomized denominator file. The study will target a sample size of 825 dentist participants.

Dentists will be recruited primarily through email containing a brief description of the study and a link to the study questionnaire. Meetings will be held with Regional Node Coordinators to review recruitment issues and enrollment progress and strategize follow-up methods to enhance participation toward achievement of targeted recruitment.

We will recruit a target of 50 responders to participate in a survey retest within approximately 1-2 weeks of completing the questionnaire to measure item internal validity.

Compensation

Participants who wish to receive compensation and can accept payment will be remunerated \$50 for completing the electronic questionnaire. If participants complete the test-retest of the electronic questionnaire, they will be remunerated an additional \$50. Payment will be sent to participants following the conclusion of the study.

5.3 Participant Withdrawal

5.3.1 Reasons for Participant Withdrawal

Participants can choose not to participate in the study and are free to withdraw, i.e., not complete the questionnaire, at any time without penalty.

5.3.2 Handling of Participant Withdrawals

It is anticipated that participants will not be replaced since the invitation numbers are based on prior Network recruitment experience. Participants who withdraw participation prior to completion of the questionnaire will not receive remuneration. Practitioners who contact network staff requesting withdrawal from further SUDS activities will be placed on a do not contact list and removed from study-related email communications.

5.4 Premature Termination or Suspension of Study

This study may be suspended or prematurely terminated if there is sufficient reasonable cause. The PI is responsible for promptly notifying all parties and providing the reason(s) for the termination or suspension.

Circumstances that may warrant termination include, but are not limited to:

- Insufficient adherence to protocol requirements.
- Data that are not sufficiently complete and/or evaluable.
- Determination of futility.
- Determination of unexpected, significant, or unacceptable risk to study participants.

6 STUDY SCHEDULE

6.1 Phase 1, Part A – Recruitment of Practitioners into the Study

- Eligible dentists will be identified from responses to the Network Enrollment Questionnaire and will be invited to participate based on inclusion criteria.
- A stratified random sample will be taken. The sample will be stratified based on regional membership to ensure representation of practitioners across the US. To provide adequate representation of practitioners working with adolescent patients, pediatric dentists will be oversampled.
- Agreement to complete the questionnaire will indicate that study participants have read the consent information, and this will imply tacit consent. A waiver of signed consent will be requested from the IRB.

Phase 2, Part B- Retest of the Questionnaire

- Dentists selected from among those study participants who completed the questionnaire will be emailed a second online questionnaire request approximately two weeks after the receipt of their first completed questionnaire.
- Dentists will be sampled for the retest until n=50 retest completions are achieved.
- Completion of the retest questionnaire will indicate implied consent.

6.2 Phase 2, Merging Study Questionnaire with Enrollment Questionnaire and Completion of Data Analyses

- Study questionnaire and Network enrollment questionnaire data will be linked using participant IDs.
- Contact information will be removed from the final merged dataset and data will be stored/saved using Unique Participant IDs.
- Data Analyses will be completed as described in Section 11.3 Final Analysis Plan.

Document Owner: SUDS Study PI & Study Manager

7 STUDY PROCEDURES/EVALUATIONS

Questionnaire Development

This questionnaire was developed through an iterative process that consisted of: (1) a scoping literature review; (2) development of a brief overview of the state of science related to substance use screening recommendations in outpatient healthcare settings; (3) formation of an ad-hoc advisory board consisting of the Network PEC and ad-hoc members with relevant expertise in substance use screening in dental settings; (4) solicitation of key topics to be covered and questions to be answered by the practitioner questionnaire from the Advisory committee; and (5) consultation with topical experts in adolescent substance use screening and assessment. Once the questionnaire items were drafted, it was submitted for full Advisory Board review and edited until a consensus document was developed. This consensus document was reviewed and approved by the NIDCR program official. The questionnaire has undergone review by the NCC to ensure it is psychometrically sound and to ensure the data it collects will allow for adequate evaluation of study objectives.

Questionnaire User Testing

The NCC will perform internal testing of the electronic study questionnaire, including internet browser compatibility. Study team members (e.g., SPI, National Network Director, Regional Directors, etc.) and other approved Network collaborators will be given the opportunity to externally test the website prior to administration to study participants.

Questionnaire Administration

According to the inclusion criteria, eligible participants, i.e., Network dentists will be identified from their responses to the Network's enrollment questionnaire.

Consistent with regulations outlined by the University of Alabama at Birmingham IRB and regional/local IRBs, information about the study will be provided to all eligible participants via an information sheet/questionnaire link in the email invitation.

After the initial invitation and follow-up email reminders, the NCs will systematically contact non-responders, and participants with incomplete information, by email, phone, or fax to encourage questionnaire completion. If no feedback is received or the participant does not complete the questionnaire after these follow-up attempts, it will be assumed the practitioner is not interested in the study. Node Coordinators may also contact participants as part of data cleaning conducted by the NCC. Once target recruitment is achieved (N= 825 Dentists), the questionnaire will be closed to participation.

8 ASSESSMENT OF SAFETY

8.1 Definitions of Safety Parameters

8.1.1 Unanticipated Problems

The Office for Human Research Protections (OHRP) considers unanticipated problems involving risks to subjects or others to include, in general, any incident, experience, or outcome that meets all following criteria:

- Unexpected in terms of nature, severity, or frequency given (a) the research procedures that are described in the protocol-related documents, such as the IRBapproved research protocol and informed consent document; and (b) the characteristics of the subject population being studied;
- Related or possibly related to participation in the research (possibly related means there is a reasonable possibility that the incident, experience, or outcome may have been caused by the procedures involved in the research); and
- Suggests that the research places subjects or others at a greater risk of harm (including physical, psychological, economic, or social harm) than was previously known or recognized.

8.2 Specification of Safety Parameters

Safety monitoring for this study will focus on unanticipated problems involving risks to participants.

8.3 Reporting Procedures

8.3.1 Unanticipated Problem Reporting

Per Network procedures, unanticipated incidents and events will be reported to the PI. After the PI is made aware of the incident/event, the following procedures will be followed.

Incidents or events that meet the OHRP criteria for unanticipated problems require the creation and completion of an unanticipated problem report form. OHRP recommends that investigators include the following information when reporting an adverse event, or any other incident, experience, or outcome as an unanticipated problem to the IRB:

- Appropriate identifying information for the research protocol, such as the title, investigator's name, and the IRB project number;
- A detailed description of the adverse event, incident, experience, or outcome;
- An explanation of the basis for determining that the adverse event, incident, experience, or outcome represents an unanticipated problem;

• A description of any changes to the protocol or other corrective actions that have been taken or are proposed in response to the unanticipated problem.

To satisfy the requirement for prompt reporting, unanticipated problems will be reported using the following timeline:

- Unanticipated problems will be reported to the IRB as soon as possible but in all cases within 10 working days of the investigator becoming aware of the problem.
- All unanticipated problems should be reported to appropriate institutional officials (as required by an institution's written reporting procedures), the supporting agency head (or designee), and OHRP within one month of the IRB's receipt of the report of the problem from the investigator.

All unanticipated problems will be reported to NIDCR concurrently with reporting to the IRB. These reports will be made to NIDCR's centralized reporting system via the Clinical Research Operations and Management Support (CROMS) contractor:

- Product Safety Fax Line (US): [name]
- Product Safety Fax Line (International): [contact]
- Product Safety Email: rho [contact]

9 STUDY OVERSIGHT

The PI will be responsible for study oversight, including monitoring safety, ensuring that the study is conducted according to the protocol and ensuring data integrity. The NCC will provide the PI with current data summaries, and the PI will review the data for safety concerns and data trends at regular intervals and will promptly submit reportable events to the IRB and NIDCR that arise during the conduct of the study, per the IRB's reporting time-frame requirements. To ensure data integrity, the PI, NCC, and study team will adhere to data quality management processes (please see Section 13).

10 CLINICAL SITE MONITORING

No outside clinical site monitoring will be employed for this study. The NCC is responsible for launching the study and collecting data received as part of the study. Quality Assurance/Quality Control activities associated with data collection and processing will be outlined in the Data Management Plan. The NCC will ensure that the quality and integrity of the study data and data collection are maintained. The NIDCR reserves the right to conduct independent clinical site monitoring as necessary.

11 STATISTICAL CONSIDERATIONS

11.1 Study Hypotheses

The primary objective of this study is to conduct a national survey of dentists to assess knowledge and behavior related to substance use screening practices. As such, formal hypothesis testing will not be conducted to achieve the study objectives.

11.2 Sample Size Considerations

Given that the primary analysis is descriptive, the power analysis was based on generating 95% confidence interval widths (i.e., margin of error typically reported with survey and polls) with 80% power. With a sample size of 825 participants, means will have 95% confidence interval widths of .136 standard deviation units (i.e., ±.068 standard deviation units around the mean). Because confidence interval widths for proportions are dependent on the value of the proportions, we estimated the widths for proportions of 0.10, 0.25, 0.50, 0.75, and 0.90. These estimates are listed in the table below:

Proportion	95% Confidence Interval		
.100	.080	.123	
.250	.221	.281	
.500	.465	.535	
.750	.719	.779	
.900	.877	.920	

All power analyses were carried out using PASS 2023.¹⁰⁷

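### Section 11.2 attaches "80% power" to confidence-interval widths that are plain 95% intervals at n = 825 and contain no 80% term

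*Protocol*

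**What the plan says.** Section 11.2 of the protocol (Sample Size Considerations) bases the sample size on precision because the primary analysis is descriptive. It says that "the power analysis was based on generating 95% confidence interval widths (i.e., margin of error typically reported with survey and polls) with 80% power".

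For means it reports that "means will have 95% confidence interval widths of .136 standard deviation units (i.e., ±.068 standard deviation units around the mean"). For proportions it says "we estimated the widths for proportions of 0.10, 0.25, 0.50, 0.75, and 0.90" and tabulates five 95% intervals: .080 to .123, .221 to .281, .465 to .535, .719 to .779 and .877 to .920. The software named is PASS 2023.

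The section gives no target width, no assurance or tolerance probability, and no hypothesis to which the 80% could belong. Section 11.1 adds that "formal hypothesis testing will not be conducted to achieve the study objectives".

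**The concern.** Power is the probability that a test rejects a stated null hypothesis under a stated alternative. A confidence-interval width has none. The nearest meaningful reading is assurance: the probability that the interval computed from the data will be no wider than the planned one. That is a legitimate design target, but it requires a calculation that allows for sampling variation in the standard deviation or the observed proportion.

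Section 11.2 is the protocol's only justification for 825 participants, and precision is its only design criterion. If the 80% was never used, the section credits its figures with a property that was not computed. A reader may take it as a guarantee about the margins of error that will be reported.

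**Working it through.** **Inputs** (all from Section 11.2): n = 825; two-sided 95% confidence; half-width .068 SD and full width .136 SD for means; proportions .10, .25, .50, .75 and .90; claimed power 80%.

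**Step 1. Reproduce the figures for means without any 80% term.**

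- Half-width = 1.96/√825 = 1.96/28.723 = .0682 SD.
- Full width = 2 × .06824 = .1365 SD (.13647 before rounding).

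These are the protocol's .068 and .136. Using the t quantile on 824 degrees of freedom (1.9628) gives a full width of .1367.

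**Step 2. Reproduce the table for proportions.** Clopper-Pearson limits at n = 825 with x = np (not rounded to an integer):

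| p | Computed | Tabled | Width, unrounded |
|---|---|---|---|
| .10 | .0804 to .1225 | .080 to .123 | .0421 |
| .25 | .2208 to .2810 | .221 to .281 | .0602 |
| .50 | .4653 to .5347 | .465 to .535 | .0693 |
| .75 | .7190 to .7792 | .719 to .779 | .0602 |
| .90 | .8775 to .9196 | .877 to .920 | .0421 |

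All ten limits agree to three decimals (the upper limit at .10 is .12253 and the lower limit at .90 is .87747 before rounding). The 80% plays no part in any figure.

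**Step 3. Read the 80% as assurance, for means.** The realised half-width is t × s/√n. With the true SD set to 1 and normal data, the chance that it is at most h is P(χ²₈₂₄ ≤ 824 × (h√825/1.9628)²).

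- h = .0680 (printed value taken as exact): P(χ²₈₂₄ ≤ 815.9) = 43%.
- h = .0682 (unrounded): P(χ²₈₂₄ ≤ 821.6) = 48%.
- h = .0685 (upper edge of what prints as .068): P(χ²₈₂₄ ≤ 827.9) = 54%.

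No rounding of the stated figure comes near 80%.

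**Step 4. Half-width for means that does carry 80% assurance at n = 825.** The 80th percentile of χ²₈₂₄ is 857.96, and √(857.96/824) = 1.0204. The half-width is 1.9628/28.723 × 1.0204 = .0697 SD, so about ±.070 SD and a full width of .139 SD. Relative to the stated calculation, .1395/.1365 = 1.022, about 2% wider.

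**Step 5. Same reading for proportions.** Exact binomial sum of the probability that the realised Clopper-Pearson width does not exceed the planned one:

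| p | Unrounded width | Width from tabled limits | 80%-assured width |
|---|---|---|---|
| .10 or .90 | 51% (.0421) | 68% (.043) | .0437 |
| .25 or .75 | 51% (.0602) | 42% (.060) | .0612 |
| .50 | about 100% (.0693) | about 100% (.070) | .0693 |

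At .50 the width is at its maximum, so any other observed proportion gives a narrower interval.

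**The case against.** The strongest reply is that nothing is miscalculated. Every number reproduces. The same sentence explains the widths as the margin of error that surveys usually report, which is exactly what they are. The protocol never says that the realised width will be at or below .136 SD with 80% probability; assurance is a meaning supplied by the reader. On this view the fault is one stray phrase.

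Most of that stands. The arithmetic is sound, and the criticism has to be that the phrase is undefined and unused, not that a defined guarantee was broken. It does not rescue the sentence. The primary analysis has no hypothesis for the power to refer to, and the only sensible alternative meaning is not met for means or for four of the five proportions.

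Four stronger readings are tempting, and the protocol does not support them:

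- **That every stated width has only about even odds.** The .50 row is met almost surely, and the .10 and .90 rows as tabled are met 68% of the time.
- **That the 43% is a firm figure.** It treats a rounded .068 as a hard limit; the unrounded value gives 48%.
- **That the survey is too small.** Holding the stated mean width with 80% assurance would take 861 participants at the unrounded width, or 867 at .136 taken as exact. That is 4% to 5% more, and nothing in the protocol requires this assurance.
- **That missing power figures for the secondary tests in Section 11.3 are part of the error.** Sizing a descriptive survey on its primary precision is legitimate, and detectable effects for secondary tests can be left to a statistical analysis plan.

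**Conclusion.** The point holds as a misdescription. Section 11.2 attributes 80% power to widths that were computed without it. Read as assurance, the statement is wrong for means and for proportions of .10, .25, .75 and .90, and right only for .50.

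The practical size is small: about 2% in the width for means (±.070 instead of ±.068 SD), and .001 to .002 in the affected proportion widths. No planned analysis changes, and the adequacy of 825 participants is not in question.

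The assurance figures assume simple random sampling, 825 complete responses per item, normal data for the means, and Clopper-Pearson intervals for the proportions. That the figures contain no 80% term depends on none of these beyond the interval formulas that reproduce them.

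**What to change.** Either of two one-sentence edits to Section 11.2 is enough.

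1. Delete the reference to 80% power and describe the figures as expected 95% confidence-interval widths at n = 825 under simple random sampling. All printed numbers stay. This is the simpler choice and suits a descriptive survey.
2. Keep an 80% statement but define it as the probability that the realised interval is no wider than stated. The precision for means then becomes ±.070 SD (width .139), and the proportion widths become about .044 at .10/.90 and .061 at .25/.75, with .50 unchanged.

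Keep N = 825 in both cases. The cost is a wording change; under the second option the stated precision also becomes slightly less favourable.
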